| Healthcare utilization related to MF-CTCL (as assessed by physician) | | |
| Hospital admissions [‡] | | X |
| Emergency room visits | | X |
| Clinical Status (as assessed by physician) | X | X |
| Clinical Status Assessments* | | |
| Composite Assessment of Index Lesion Severity | X | X |
| Modified Severity Weighted Assessment Tool | X | X |
| Physician's Global Assessment | X | X |
| Body Surface Area of disease | X | X |
| Patient-Completed Questionnaires[§] | | |
| Visual Analogue Scale for pruritus | X | X |
| Skindex-29 | X | X |
| Mycosis fungoides / Sézary syndrome-type cutaneous T-cell lymphoma | X | X |
| Safety Measures^{**} | | |
| AEs and SAEs | X ⁺ | X |
| Reports of secondary exposures | | X [^] |

*Included in pre-treatment data collection, which is performed at enrollment. All data must be completed as available.

[†]Includes collection of start and stop dates for each medication, including reasons for starting and stopping medications. Start and stop dates are also collected for Valchlor, including short gaps in treatment, such as drug holidays.

[‡]For each hospital admission, length of stay and primary admission and discharge diagnoses will be collected.

[§]To be completed by patients who can read and understand English and are able to self-complete the questionnaires based on the investigator's assessment. Patients who are unable to self-complete the questionnaires will not be excluded from the study.

^{**}Safety measures, which include AEs and SAEs, will be collected from the informed consent date and prospectively at every visit during the study and up to 30-days post-discontinuation of Valchlor during the study. Ongoing AE and SAE data will be collected through the end of study, regardless of Valchlor use.

New AEs and SAEs that occur more than 30 days after discontinuation of Valchlor will be reported to Actelion US Drug Safety if investigator feels there is a possible causal relationship with Valchlor. Investigators are also expected to assess patients for AEs and SAEs and follow the appropriate reporting procedures per Section 7.

⁺All ongoing AEs and SAEs for patients being treated [see Section 5.2.1 for definition of “being treated”] with Valchlor.

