5.7.5 Adverse events

The frequency and percentage of patients experiencing any on-study AEs, SAEs, or death will be summarized by system organ class and preferred MedDRA terminology. Additional detail for AEs of special interest (e.g., dermatitis) will be summarized separately. SAEs will be displayed in patient listings, both including and excluding events that were not concurrent with Valchlor exposure. The definition of an on-study event is one that occurs on the day of enrollment or later, but before the date of study discontinuation or completion.

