## ANALYSIS OBJECTIVES

The objectives of the MF-CTCL prospective cohort study are:

- To describe clinical characteristics of patients treated with Valchlor at enrollment and during the 2 year study observation period.
- To describe treatment and response assessment patterns of patients with MF-CTCL treated with Valchlor at enrollment and during the study observation period.
- To assess outcomes (e.g., clinical status and rates of healthcare utilization [MF-CTCL-related hospitalizations and emergency room visits]) in patients with MF-CTCL treated with Valchlor during the study observation period.
- To collect and describe the incidence of AEs/SAEs in patients with MF-CTCL treated with Valchlor:
  - To estimate the incidence of dermatitis in patients using Valchlor during the study observation period.
  - To describe the management of dermatitis in patients using Valchlor at enrollment and during the study observation period.
- To collect patient-completed symptoms and QOL questionnaires.

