### **Exposure Definitions and Measures**

Start of observation is defined as date of enrollment.

End of observation is defined as End Of Study (EOS), which includes, adverse event, patient withdrew consent, patient lost to follow-up, physician's decision to withdraw or study completion, whichever occurs first.

Total exposure time is defined as the date of first Valchlor exposure to the date of last Valchlor exposure.

Total on-study Valchlor exposure time is defined as the first day of Valchlor use to last day of Valchlor use during the observation period. If the patient was using Valchlor at the end of observation, the last on-study day of Valchlor use is equal to the end date of observation period.

Patients may discontinue Valchlor while on study. In this case, the last day of Valchlor exposure will be when the patient discontinues Valchlor (as reported on the Valchlor treatment log). Patients who restart Valchlor after discontinuing will then begin adding Valchlor exposure days once Valchlor is restarted through the end of the study. For the patients that restart Valchlor during the study, the Total on-study Valchlor exposure will be a sum of all days in which Valchlor was dosed during the study, as reported on the Valchlor treatment log.

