**Skindex-29, Functioning**

Baseline Completed [(mean +/- SD) (min, max)]	n= xx.x +/- xx.x (xx,xx)				
Baseline Not Done [(mean +/- SD) (min, max)]					

Follow-Up Completed	n=	n=	n=	n=	n=
---------------------	----	----	----	----	----

Quarter 1 [(mean +/- SD) (min, max)]	xx.x +/- xx.x (xx,xx)				
Quarter 2 [(mean +/- SD) (min, max)]					
Quarter 3 [(mean +/- SD) (min, max)]					
Quarter 4 [(mean +/- SD) (min, max)]					
Follow-Up Not Done [(mean +/- SD) (min, max)]					

- 
- a. Patients can contribute multiple visits to a quarter. These visits could be categorized as response or non-response for the same patient within a quarter.

Run Date: ddMMMyyyy

Date of Data Extraction: ddMMMyyyy

Helsinn Therapeutics (US),  
 Inc., Protocol AC-079A501  
 (PROVe)

Table 18. Adverse Events

Characteristic	V+C+ Other	V+P+ Other	V+OB+ Other	V+ Other
	n=		n=	n=
Overall a	xx (xx.x)		xx (xx.x)	xx (xx.x)
System Organ Class 1				
Preferred Term A				
Preferred Term B	xx.x +/- xx.x		xx.x +/- xx.x	xx.x +/- xx.x
...				
System Organ Class 2				
Preferred Term C	xx (xx.x)		xx (xx.x)	xx (xx.x)
...				
...				

---

Note: Number of subjects and % of subjects are shown

a. Overall refers to any recorded AE, including AEs reported as ongoing at the time of enrollment

Run Date: ddMMMyyyy

Date of Data Extraction: ddMMMyyyy

Helsinn Therapeutics (US), Inc.,  
 Protocol AC-079A501 (PROVe)  
 Table 19. Serious Adverse Events

Characteristic	V+C+ Other	V+P+ Other	V+OB+ Other	V+ Other
	n= xx (xx.x)	n= xx (xx.x)	n= xx (xx.x)	n= xx (xx.x)
Overall a				
System Organ Class 1				
Preferred Term A				
Preferred Term B	xx.x +/- xx.x	xx.x +/- xx.x	xx.x +/- xx.x	xx.x +/- xx.x
...				
System Organ Class 2				
Preferred Term C	xx (xx.x)	xx (xx.x)	xx (xx.x)	xx (xx.x)
...				
...				

Note: Number of subjects and % of subjects are shown

a. Overall refers to any recorded AE, including AEs reported as ongoing at the time of enrollment

Run Date: ddMMMyyyy

Date of Data Extraction: ddMMMyyyy

Table 20. Continuous vs. Non-Continuous Exposure

Characteristic	Overall	Continuous Exposure (n=xx)	Non-Continuous Exposure (n=xx)
Total days of exposure, mean (SD)	xx.x (xx.x)	xx.x (xx.x)	xx.x (xx.x)
Days of longest continuous exposure, mean (SD)	xx.x (xx.x)	xx.x (xx.x)	xx.x (xx.x)

Helsinn Therapeutics (US), Inc.,  
 Protocol AC-079A501 (PROVe)

Table 21. Percent of patients with  $\geq 50\%$  reduction from baseline in % Body Surface Area of disease at 12 months ( $365 \pm 90$  days)

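### The Overall row of SAP Tables 18 and 19 counts adverse events already ongoing at enrollment, contrary to the on-study rule in Protocol 5.7.5, and no other table supplies the on-study figure

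*SAP*

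**What the plan says.** Protocol 5.7.5 sets the AE analysis: "The frequency and percentage of patients experiencing any on-study AEs, SAEs, or death will be summarized by system organ class" and preferred term. It then defines the term: "The definition of an on-study event is one that occurs on the day of enrollment or later", with the upper limit that the event precedes study discontinuation or completion. The same section promises a separate summary for events of special interest, with dermatitis as the example.

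The SAP's Analysis Objectives include "To collect and describe the incidence of AEs/SAEs in patients with MF-CTCL treated with Valchlor" and, beneath it, "To estimate the incidence of dermatitis in patients using Valchlor during the study observation period". Under Exposure Definitions and Measures the SAP adds: "Start of observation is defined as date of enrollment".

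Events present before that date are nonetheless in the database. The footnote to the enrollment-visit safety entry in Protocol Table 1 calls for "All ongoing AEs and SAEs for patients being treated" with Valchlor.

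The AE paragraph in the SAP's Statistical Methods omits the on-study restriction. In SAP Appendix A, Tables 18 and 19 state that "Number of subjects and % of subjects are shown", and footnote a, attached to the Overall row of each, reads: "Overall refers to any recorded AE, including AEs reported as ongoing at the time of enrollment".

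**The concern.** An event already present when observation starts is prevalent, not incident. The footnote puts such events into the headline safety percentage, although the protocol's own analysis section restricts that summary to on-study events. The SAP neither acknowledges nor justifies the change.

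The matter is not trivial in this cohort. Continuing users have had more than 30 days of Valchlor before enrollment, and the SAP's Assessment Schedule describes the ongoing events collected at enrollment as related to Valchlor. The events added may therefore be the reactions the study sets out to quantify.

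The mixed figure is not cumulative incidence since starting Valchlor either. Patients must be on Valchlor at enrollment, so people who had already stopped because of a reaction are absent, and a continuing user's reaction that had resolved by enrollment is not an ongoing event. The percentage answers neither question cleanly.

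**Working it through.** The documents state no AE rate and no count of AEs ongoing at enrollment, so there is no figure to reproduce. The check is a comparison of texts, followed by what can be said about direction and size.

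**1. The counting rules side by side**

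| Source | Events counted |
|---|---|
| Protocol 5.7.5 | From the day of enrollment, before discontinuation or completion |
| SAP Tables 18 and 19, Overall row (footnote a) | All on record, with those ongoing at enrollment included |
| SAP Tables 18 and 19, system organ class and preferred-term rows | No onset rule stated |
| SAP Statistical Methods, AE paragraph | No onset rule stated |
| SAP Healthcare Resource Utilization | Post-enrollment hospitalizations and ER visits only |

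The first two rows cannot both be followed. The last row shows that the SAP applies the post-enrollment restriction where it chooses to.

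**2. Is the on-study figure given elsewhere?** The list of shells in SAP Appendix A has two AE tables (18 and 19). Neither they nor any other table is specific to dermatitis. Listings 1, 2, 3 and 9 show individual events, not percentages. The columns of Tables 18 and 19 are the concomitant-therapy groups, with no split into continuing and new users, so a reader of the tables cannot separate prevalent from new events.

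**3. Direction.** Let p be the share of patients with at least one on-study AE, and q the share with at least one AE ongoing at enrollment. The Overall row reports

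T = P(on-study or ongoing), with max(p, q) ≤ T ≤ min(1, p + q).

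Since T ≥ p always, the error cannot be downward. T exceeds p as soon as one patient's only AE is an ongoing one that does not qualify as on-study. T = p if every patient with an ongoing AE also has an on-study AE.

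**4. Size, as illustration only.** Both p and q are assumed. If the two are independent, T = p + q(1 − p):

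| p | q = 5% | q = 10% | q = 20% | q = 30% |
|---|---|---|---|---|
| 10% | 14.5% | 19.0% | 28.0% | 37.0% |
| 30% | 33.5% | 37.0% | 44.0% | 51.0% |
| 50% | 52.5% | 55.0% | 60.0% | 65.0% |

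For example, with p = 30% and q = 20%, T = 0.30 + 0.20 × 0.70 = 0.44. Without independence, the same inputs allow anything from 30% to 50%. Across the grid the excess under independence runs from 2.5 points (p = 50%, q = 5%) to 27 points (p = 10%, q = 30%). A range this wide shows that the documents do not fix the size.

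**5. Who contributes to q.** Continuing users do. New initiators can too: the protocol enrolls them at their first office visit after starting Valchlor, the SAP allows up to 30 days between start and enrollment, and ongoing events are recorded for all treated patients. So q is a weighted sum over both groups, and the share of continuing users alone does not determine it.

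**The case against.** The strongest reply is that nothing is hidden. The tables are titled simply as adverse events and serious adverse events, the footnote discloses the rule, and Listing 9 carries onset dates. The protocol is also not uniform: the Data Analysis part of its synopsis, like the SAP's methods text, speaks of any AEs or SAEs without the on-study limit. These observations are correct. But section 5.7.5 is the detailed rule and the one that defines the term. Disclosure does not supply the missing on-study percentage, and a listing is not an incidence estimate.

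Other parts of the reply limit how far the point reaches. A reader might infer four stronger things that the documents do not support:

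- *That every row of both tables counts ongoing events.* Footnote a is attached to the Overall row only. For the rows where dermatitis would appear, the SAP is silent; inclusion there is plausible but not stated.
- *That the inflation has a known size, driven by continuing users.* No rate is given, and new initiators can bring ongoing events as well.
- *That the whole AE/SAE objective is confined to the observation period.* Those words stand only in the dermatitis sub-objective; the general AE/SAE objective has no time limit.
- *That 5.7.5 requires onset after enrollment.* It speaks of an event occurring, not of onset. Under Protocol 7.1.1, a persistent condition present at enrollment that worsens after the study starts is itself an AE. A strict onset filter could drop such events and understate the on-study figure.

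**Conclusion.** The point stands as a conflict between the SAP's Overall-row footnote and Protocol 5.7.5, together with a gap: no onset rule for the other rows and no on-study or dermatitis-specific output anywhere in the table shells. The conflict rests on the texts and needs no assumption. Nor does the direction, because the set the footnote counts contains the on-study set. The size is undetermined; the illustrated 2.5 to 27 points rest wholly on assumed rates and independence, and the true excess could be zero. The correction should be made before the tables are used to report incidence.

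**What to change.** Apply the Protocol 5.7.5 definition to all rows of Tables 18 and 19: Overall, system organ class and preferred term, dermatitis terms included. Count an event if its onset is on or after the day of enrollment and before study discontinuation or completion, or if it was ongoing at enrollment and worsened afterwards (Protocol 7.1.1). Show the remaining ongoing events in a separate, labelled row or column. Rewrite footnote a to match, and in Table 19 refer to SAEs where the footnote now says AE.

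Two details need a sentence each in the SAP. First, how worsening is identified: Listing 9 shows onset date and intensity but no date of worsening, so the rule should say whether a worsening was entered as a new record. Second, how an incomplete AE onset date is handled, since the SAP's date-imputation table has no entry for it.

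The cost is a footnote change and a date filter on data already collected. The reported percentages may be lower.

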| | 
from the date of signed informed consent (enrollment) until end of study, which includes withdrawal of consent, loss to follow-up, death, or study completion. Continuation in the study is not contingent on continuation of Valchlor.
 
Patients currently enrolled and ongoing or newly enrolled will be offered to participate in the 24-month study of this protocol Amendment 1. Patients who enrolled under the original protocol (prior to Amendment 1) and are still ongoing in the study will be re-consented and to follow data collection specified in Table 1 of this protocol for a total of 24 months from original consent date. Patients who enrolled and have completed 1 year of the study under the original protocol will not be re-consented under Amendment 1.
 |
| 
POPULATION (SETTING AND STUDY POPULATION)
 | 
This study will enroll approximately 300 consecutive patients diagnosed with MF-CTCL and being treated with Valchlor, regardless of other MF-CTCL therapies received before or at enrollment. Patients will be enrolled from up to 50 participating centers/clinics in university-affiliated or community hospitals in the US. The participation of physicians and patients in the study is on a voluntary basis.
 
Inclusion criteria:
 
 • All adult patients (≥ 18 years of age) diagnosed with MF-CTCL and being treated with Valchlor. This includes patients newly initiating Valchlor OR patients continuing treatment with Valchlor: 
 ○ Patients newly initiating Valchlor are patients who have their first office visit after having initiated Valchlor. ○ Patients continuing treatment with Valchlor includes patients who are actively taking Valchlor on the day of enrollment. ○ Signed patient informed consent. 
Exclusion criteria:
 
 • None |
| 
VARIABLES
 | 
The variables of interest for this study includes clinical characteristics, treatment patterns, clinical status, as assessed by the physician (including the methods used in practice to assess clinical status), MF-CTCL-related healthcare utilization, as assessed by the physician (hospitalizations and emergency room visits), AEs and
 |

| | |
|--|---|

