5.3.2 Exposure definition and measures

Start of observation is defined as date of signed informed consent.

End of observation is defined as EOS, including death, withdrawal of consent, loss to follow-up, or study completion, whichever occurs first.

Total exposure time is defined as the date of first Valchlor exposure to the date of last Valchlor exposure.

Total on-study Valchlor exposure time is defined as the first day of Valchlor use to last day of Valchlor use during the observation period. If the patient was using Valchlor at end of observation, the last on-study day of Valchlor use is equal to the end date of observation period. Drug holidays are excluded from the sum of exposure time.

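### SAP Table 20 compares mean Valchlor days between undefined continuous and non-continuous groups over unequal follow-up, so the contrast cannot be interpreted

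*SAP*

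**What the plan says.** SAP Appendix A contains the shell "Table 20. Continuous vs. Non-Continuous Exposure". It has an overall column and one column per group. Its two rows are the mean (SD) of total exposure days and the mean (SD) of the longest unbroken run. No test, p-value footnote or commentary is attached.

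Neither document defines the two labels or sets a minimum gap. Neither says where a patient belongs who stops once and never restarts. The nearest text is in the SAP under Exposure Definitions and Measures: "Patients who restart Valchlor after discontinuing will then begin adding Valchlor exposure days once Valchlor is restarted through the end of the study". For restarters, "the Total on-study Valchlor exposure will be a sum of all days in which Valchlor was dosed during the study". Protocol 5.3.2 agrees on gaps: "Drug holidays are excluded from the sum of exposure time". Both documents also define a total exposure time running from first to last use, and Table 20 does not say which measure it takes.

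Follow-up is unequal. Protocol 5.1 allows up to 2 years, but the synopsis says: "Patients who enrolled and have completed 1 year of the study under the original protocol will not be re-consented under Amendment 1".

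Protocol 5.7.3 plans Kaplan-Meier freedom from discontinuation in newly initiated patients, with optional sensitivity analyses on gaps. The SAP has neither a method nor a shell for it. Time to next treatment (Table 25) is a different quantity.

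**The concern.** The group is fixed by something that happens after enrollment, and the quantity averaged is the time needed for it to happen. On the natural reading, a patient must use Valchlor, stop and restart under observation to be non-continuous. A patient who quits for good after three weeks has one unbroken period and falls in the continuous group. This is immortal-time (length) bias. Longer observation raises both the chance of a recorded gap and the number of days on drug, so mixing 12- and 24-month patients adds to it.

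Drug holidays and time from initiation to discontinuation are named variables of interest (protocol 5.3.1). A reader could take a difference in Table 20 as evidence on whether interrupting Valchlor goes with longer or shorter use, when it may reflect only how the groups were formed.

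**Working it through.** Table 20 is an empty shell, so there is no planned figure to reproduce. The check is what the table would show if gaps and permanent stopping were unrelated.

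**Inputs from the documents**
- Permanent stopping: the SAP (Analysis Populations) says patients who permanently discontinued and switched therapy, 15–20%, are left out at 12 months. I use this as the proportion stopping by month 12. It is an approximation, since patients who stopped without switching may be extra. As a yearly rate, −ln(1 − 0.15) = 0.16 and −ln(1 − 0.20) = 0.22.
- Follow-up: protocol 5.5 needs 270 evaluable patients and projects about 200 under Amendment 1. I take 200/270 = 74% at 730 days and 70/270 = 26% at 365 days.
- Gap days do not count as exposure (protocol 5.3.2 and the SAP's on-study definition).

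**Assumptions, not in the documents**
- 0.3 or 0.6 gaps per year on drug, of 30, 90 or 180 days.
- Constant, independent rates of gaps and of permanent stopping.

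**Method.** 300,000 simulated patients per setting. Non-continuous means at least one stop followed by a restart under observation; everyone else is continuous. A continuous user has a single run, so total days and longest run are equal.

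| Gap (fixed) | Stop by month 12 | Gaps/year | Continuous, mean days | Non-continuous, mean days | Difference | Ratio | Longest run, non-continuous |
|---|---|---|---|---|---|---|---|
| 30 d | 15% | 0.3 | 508 | 595 | +87 | 1.17 | 427 |
| 30 d | 15% | 0.6 | 463 | 578 | +115 | 1.25 | 396 |
| 30 d | 20% | 0.3 | 478 | 582 | +104 | 1.22 | 417 |
| 30 d | 20% | 0.6 | 430 | 564 | +134 | 1.31 | 386 |
| 180 d | 15% | 0.3 | 507 | 458 | −49 | 0.90 | 339 |
| 180 d | 15% | 0.6 | 465 | 430 | −35 | 0.92 | 314 |
| 180 d | 20% | 0.3 | 478 | 449 | −29 | 0.94 | 333 |
| 180 d | 20% | 0.6 | 435 | 421 | −14 | 0.97 | 307 |

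**Variations**
- Fixed 90-day gaps: +26 to +66 days.
- All patients followed 24 months, 30-day gaps: +65 to +132 days (ratio 1.11 to 1.27), so unequal follow-up is not the only source.
- Gaps of random length averaging 180 days: +4 to +41 days with the 74/26 mix, and −35 to +12 with everyone at 24 months. Near that length the sign depends on the spread of gap lengths.
- Longest run: the continuous group is longer in every setting above, by 44 to 82 days at 30-day gaps and 128 to 168 days at fixed 180-day gaps.
- Gap days counted (first-to-last-use span): +110 to +174 days at 15–20% stopping, for mean gaps of 14 to 180 days.
- Any stop counted as non-continuous, 30-day gaps: −65 to −142 days with the 74/26 mix and −168 to −235 with everyone at 24 months. With equal follow-up this holds by definition, because the continuous group is then exactly those on drug to the end.

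**Does the grouping cause it?** Take patients on Valchlor at day 180, group them by gaps up to that day, and compare later days on drug. With 15–20% stopping, a 30% chance of a first gap by month 12, mean gaps of 14 to 90 days and a 2/3 : 1/3 follow-up mix, the difference is −3 to +2 days. Table 20's contrast in the same settings is +55 to +126 days.

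**The case against.** The strongest reply is that Table 20 is a two-row descriptive shell. It has no test and no interpretation, and no primary or secondary endpoint uses it. Persistence belongs to the protocol's Kaplan-Meier analysis, and defining the labels with a cautionary footnote might be enough. The description is fair, and it limits this point to a cheap improvement. It does not make the contrast readable. A label definition only selects which distortion the table shows, and the Kaplan-Meier analysis that would answer the question has no place in the SAP.

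Three stronger readings are tempting, and the documents do not support them.
- *A reader might infer that interrupters must look longer-treated by construction.* The SAP never says that early quitters count as continuous; that is the natural reading, not a stated rule. Even on that reading gap days are subtracted, so long gaps or very little permanent stopping can reverse the sign.
- *A reader might infer a distortion of 1.5-fold or more.* That needs heavier stopping. At 0.5 stops and 0.6 gaps per year with 30-day gaps the means are 325 and 505 days (505/325 = 1.55), but 0.5 per year means 1 − exp(−0.5) = 39% stopped by month 12, well above the SAP's 15–20%.
- *A reader might infer that the longest-run row is inflated in the same direction.* At 15–20% stopping it favours continuous users.

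**Conclusion.** The point holds as a minor one. With no true link between gaps and persistence, the natural reading makes interrupters look about 1.2–1.3-fold longer-treated with 30-day gaps, or roughly +70 to +130 days across the follow-up patterns tried. The other reading reverses the contrast, and so do fixed 180-day gaps. The two rows of the table can also point in opposite directions. A contrast whose sign depends on an unstated definition and an unknown gap length carries no usable information about interruption.

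The size rests on reading the SAP's 15–20% as stopping by month 12, on the 200-of-270 follow-up split, and on assumed gap frequency and length. No endpoint is affected. The point is worth acting on because drug holidays and discontinuation are stated interests and no other shell addresses interruption directly.

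**What to change.** - Define the minimum gap length, and state whether Table 20 uses total or on-study exposure.
- Replace the two columns with three groups at a fixed horizon of 12 months from enrollment, among patients observed that long: no gap and still on Valchlor, gap and restarted, stopped for good. Report the proportion in each group and Valchlor days within the horizon.
- Report gaps per patient-year on Valchlor for the whole cohort.
- Add the protocol 5.7.3 Kaplan-Meier freedom from discontinuation to the SAP methods and shells.
- Do not compare mean total days by gap status over unequal follow-up.

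The cost is one revised shell and one added shell. The start and stop dates are already in the Valchlor Treatment Log. The downside is that patients observed for less than 12 months contribute only to the gap rate and, if newly initiated, to the Kaplan-Meier estimate.
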